5.2.3. End of the study

The follow-up period ends after recording any complications at 15±4 days via a phone call with the patient, and then at 1 month during the follow-up visit with the surgeon.

5.3. Study Design

Steps	Inclusion Visit		Day 0 In the operating room	Day 15±4	Follow-up visit with the surgeon at 1 month
	Anesthesia consultation	Pre- anesthesia visit			
Information	X				
Consent		X			
Verification of inclusion and exclusion criteria	X	X			
Specific plantar nerve block			X		
Sensory tests			X		
ENR-Plantar nerves			X		
ENA-VVP ENA-ALR ENA-Satisfaction			X		
List of possible complications			X	X (phone call)	X

5.4. Expected duration of participant involvement, description of the timeline and duration of the study

The study itself begins when the patient and the investigator sign the consent form. It ends after checking for complications during the follow-up visit with the surgeon 1 month post-surgery.

The study is scheduled to take 24 months to complete, starting from the date of the first enrollment. The enrollment period is expected to last 23 months.

5.5. Identification of Participants

As part of this study, participants will be identified as follows:

Upon signing the consent form, the investigator logs into the secure eCeric website and creates a patient record. An alphanumeric “patient identifier” enrollment number is then automatically generated by the application. It consists of the patient's initials (first letter of the last name and first letter of the first name)

followed by a sequential enrollment number. This reference is unique and will be retained for the duration of the study.

The investigator creates an enrollment table; this table allows the patient's identity to be unambiguously linked to an enrollment sequence number. This unique number identifies the study data pertaining to the patient.

5.6. Description of measures taken to reduce or avoid bias

To avoid selection bias, this study will be offered to all eligible patients seen in the anesthesia clinic. For eligible patients who are not included, the reason for exclusion will be noted.

The evaluation criterion is sufficiently objective to avoid any assessment bias.

5.7. Description of the rules for permanently or temporarily terminating a person's participation in the research, procedures for monitoring these individuals, and procedures for replacing these subjects, if necessary

Any subject included in the study may decide to withdraw their consent to participate in the study at any time and for any reason, without having to provide explanations or justifications and without this affecting the care they are receiving or will receive. The investigator must indicate in the patient's eCRF the date and, if applicable, the reason for the termination of participation in the research. Withdrawal of consent prohibits the use of medical data obtained after the withdrawal of consent. Data already collected regarding the subject may be used.

The investigator may temporarily or permanently suspend a subject's participation in the research for any reason that impacts their safety or that is in the patient's best interest. Data already collected regarding the subject may be used in the analysis of the study results.

A subject's withdrawal from the study will not alter their usual care.

A patient who withdraws prematurely from the study will be replaced, and a study withdrawal form will be completed, including the reason for withdrawal (Consort flow diagram).

Once the protocol-specified sample size is reached, the investigator must halt recruitment for the study. However, patients who have already signed a consent form may still be included in the study.

5.8. Identification of all data collected directly in the study's eCRF and for which no other source documents exist

Sensory scores, assessment of plantar nerve recognition, patient satisfaction and comfort scores, as well as data obtained during the telephone call on Day 15±4 by a healthcare professional, are recorded directly in the eCRF.

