4.2. Secondary endpoints

Regarding Secondary Objective 1:

The feasibility of forefoot surgery using a specific block of the two distal branches of the tibial nerve, combined with a block of the superficial and deep peroneal nerves and the saphenous nerve, will be assessed by the fact that no additional anesthetic technique is required to perform the surgery.

Regarding Secondary Objective 2:

Ultrasound identification of the plantar arteries and plantar nerves below the midfoot axis will be assessed using a Numerical Scale for Identification of the Medial and Lateral Plantar Nerves (ENR-Plantar Nerves): a numerical scale ranging from 0 (no visualization) to 100 (extremely easy visualization).

Regarding Secondary Objective 3:

Patient satisfaction and comfort during the ALR procedure will be assessed using three numerical scales:

- Patient satisfaction is assessed using an Analog Numeric Scale (ANS-Satisfaction) ranging from 0 (very dissatisfied) to 100 (very satisfied).
- Pain assessment during regional anesthesia uses a Numerical Analog Scale (NAS-R) ranging from 0 (no pain) to 100 (extremely painful).
- Pain assessment during peripheral venous access (PVA) uses an ANS (ANS-PVA) ranging from 0 (no pain) to 100 (extremely painful). It will serve as a reference for the ANS-ALR.

Regarding secondary objective 4:

Any sensory-motor complications will be assessed using a questionnaire (Appendix 1) during a phone call with the patient on Day 15±4 and at 1 month during the follow-up visit with the surgeon.

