8.7. Selection of subjects to be included in the analyses

All patients approached for the study will be included in the CONSORT diagram for the study.

Any patient in the study population who has signed a consent form, completed the study, and for whom there is no protocol violation likely to critically affect the results of the analysis will be included in the analyses.

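### Patients the investigator stops for safety have no stated study follow-up (5.7) and can fall out of the completers-only analysis (8.7), so the complication rate can be understated

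*Combined protocol and SAP*

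**What the plan says.** **Stopping (5.7).** The investigator has a broad power to stop a patient: "The investigator may temporarily or permanently suspend a subject's participation in the research for any reason that impacts their safety". The sentence goes on to add the patient's best interest. For these patients the section says: "Data already collected regarding the subject may be used in the analysis of the study results". It does not say whether anything may or must be collected afterwards. It says only that leaving does not change usual care.

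**Withdrawn consent (5.7).** The one explicit bar on later data is here: "Withdrawal of consent prohibits the use of medical data obtained after the withdrawal of consent".

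**Replacement (5.7).** "A patient who withdraws prematurely from the study will be replaced, and a study withdrawal form will be completed, including the reason for withdrawal".

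**Complication follow-up (4.2, 5.2.3, 5.4, 7).** For secondary objective 4: "Any sensory-motor complications will be assessed using a questionnaire (Appendix 1) during a phone call with the patient on Day 15±4", and again at the 1-month surgeon visit. Section 5.4 ends a patient's participation after that 1-month check. Section 7 records adverse events in the eCRF at the same two contacts.

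**Who is analysed (8.7).** The rule admits "Any patient in the study population who has signed a consent form, completed the study, and for whom there is no protocol violation" likely to affect the results critically. No separate safety population is defined, and section 8.5 plans no imputation.

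**The concern.** The intervention is a single block on Day 0. Once it has been given, little study participation remains beyond the Day 15±4 call and the 1-month check, and both exist to find complications. Stopping a patient after the block therefore mostly means stopping complication follow-up.

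The ground for stopping, safety, is close to the outcome being counted. Section 5.2.2 treats paresthesia as a sign of nerve damage. A patient who reports it on Day 0 is a natural candidate for a safety stop, and is also the patient whose later answers matter most. If such patients leave the follow-up or the analysis, the loss is informative and lowers the reported rate.

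Safety is named in the primary objective, and complication follow-up is the main source of safety information after Day 0. With 50 patients, losing one or two can turn some complications into none. The point concerns the complication rate, not the Day 0 block-success endpoint.

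**Working it through.** **Step 1. Follow one patient through the text.** Suppose a patient receives the block and is then stopped by the investigator for safety, without withdrawing consent.

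- *Is later data barred?* No. The bar in 5.7 covers withdrawn consent only.
- *Is later data required?* No. Section 5.7 gives no instruction, and 4.2, 5.2.3 and 7 do not mention stopped patients. Section 5.8 lists the Day 15±4 call data as having no other source document, so a call not made cannot be recovered from the records.
- *Is earlier data usable?* Yes under 5.7. Under 8.7, read literally, no, because the patient did not complete the study. The two sections conflict.
- *Is the patient replaced?* Probably. The rule is worded for a patient who withdraws prematurely. The section heading and paragraph order suggest that investigator stops are covered, but the text does not say so.

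So 5.7 alone can lose complications that appear or are recorded after the stop. Losing the whole patient, including a complication already recorded, needs 8.7 as well.

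**Step 2. The plan's own figures.** The only precision figures are in the 8.2 table (N = 50, 95%). They follow from P ± 1.96 × √(P(1 − P)/50). At P = 0.10: 0.10 ± 1.96 × √(0.09/50) = 0.10 ± 0.083, or 0.017 to 0.183, as printed. All nine pairs of limits reproduce to three decimals. At P = 0.50 the unrounded width is 0.277 against a printed 0.278, because the table subtracts rounded limits. This point does not affect the table.

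**Step 3. Size, with assumed counts.** The documents give neither a complication rate nor a stop rate, so the counts below are assumptions. The 8.2 formula gives zero width at 0 events, so exact (Clopper-Pearson) limits are used: lower = Beta quantile 0.025 (x, n − x + 1), upper = Beta quantile 0.975 (x + 1, n − x). For 0/50 the upper limit is 1 − 0.025^(1/50) = 7.1%. Each replaced patient was also blocked, so the full denominator is 50 plus the number replaced.

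| Assumed case | Reported from completers | All blocked patients |
|---|---|---|
| Two complications, both patients stopped and replaced | 0/50 = 0% (0 to 7.1%) | 2/52 = 3.8% (0.5 to 13.2%) |
| Two complications, one patient stopped and replaced | 1/50 = 2.0% (0.05 to 10.6%) | 2/51 = 3.9% (0.5 to 13.5%) |

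**Step 4. Expected bias.** Let p be the true complication rate and q the share of patients with complications who are stopped, replaced and left out. Assume no uncomplicated patient is stopped. The expected rate among completers is p(1 − q)/(1 − pq). For p = 10% and q = 25%: 0.075/0.975 = 7.7%.

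| True rate p | q = 10% | q = 25% | q = 50% |
|---|---|---|---|
| 5% | 4.5% | 3.8% | 2.6% |
| 10% | 9.1% | 7.7% | 5.3% |
| 20% | 18.4% | 15.8% | 11.1% |

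Under this mechanism the bias is always downwards. Its size depends on q, about which the documents say nothing.

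**The case against.** The strongest reply is that 5.7 discards nothing. A reader might infer that it keeps only data gathered before the stop. The text does not say so: for investigator stops it is permissive about earlier data and silent about later data. This stands.

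A reader might also take replacement of investigator-stopped patients as settled. The sentence "A patient who withdraws prematurely from the study will be replaced" does not mention them, and a suspension can be temporary. This stands too. Replacement is a likely reading, but loss of follow-up does not depend on it.

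Third, if a complication prompts the stop, it is already known. Day 0 paresthesia and intraoperative complications are noted at the time, and the withdrawal form records the reason. Under 5.7 alone the 0/50 result would not arise. This is correct as far as 5.7 goes, but 8.7 then removes the non-completer. The withdrawal form and the flow diagram show why a patient left without putting the complication into the rate.

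Fourth, cancelling a phone call or a check protects nobody, so safety stops after the block should be rare. The 1-month contact is the surgeon's follow-up visit, which would probably take place anyway because usual care is unchanged. Both remarks are fair and limit the importance of the point. The visit taking place does not, however, ensure a study entry or inclusion in the analysis.

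Finally, the complication rate is a secondary outcome that section 8.1 analyses mainly descriptively. This also stands, and it limits the severity.

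**Conclusion.** The point holds as a gap in 5.7 combined with a conflict between 5.7 and 8.7. Followed as written, the plan can leave a patient stopped for safety without either complication check, and can exclude that patient from the complication rate even when a complication was recorded before the stop. Because the reason for stopping is related to the outcome, the rate would be too low.

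The documents do not support the stronger conclusion that 5.7 by itself erases patients with complications. It does not forbid later data after an investigator stop, and removal of the whole patient comes from the completers rule in 8.7.

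The size cannot be known from the documents. The illustrations (0/50 against 2/52, and 1/50 against 2/51) assume two complications, replacement of the stopped patients, and a literal reading of 8.7. Severity is minor to moderate: the outcome is secondary and descriptive and such stops are probably rare, but with 50 patients one or two losses change what the report says.

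**What to change.** 1. **Section 5.7, investigator stop.** State that a patient stopped by the investigator once the block has been started, and who has not withdrawn consent, still has the Day 15±4 questionnaire and the 1-month complication check. State also whether such patients are replaced.
2. **Section 5.7, withdrawal of consent.** Record on the withdrawal form whether the patient still agrees to these two checks. If not, use no later data, as the section already requires.
3. **Section 8.7.** Report complications in all patients who received any part of the block, whether or not they completed the study. Replacements add to the denominator and do not take the place of those who left. Show the number with missing follow-up. This also reconciles 8.7 with the permission in 5.7 to use data already gathered.

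The cost is protocol wording, one eCRF field and a few extra calls. Both contacts are already scheduled, so no new procedure is added. The reported rate may look less favourable.

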6. SELECTION OF RESEARCH PARTICIPANTS

6.1. Inclusion Criteria

The following patients will be included:

- Aged 18 years or older,
- Scheduled for forefoot surgery (metatarsal osteotomy, surgical treatment of ingrown toenails, foot wounds, foot infections, metatarsal fractures, or Morton's neuroma),
- Having given their consent to participate in accordance with regulations,
- Covered by social security.

6.2. Exclusion criteria

The following will not be included:

- Minors,
- Pregnant or breastfeeding women,
- Patients under guardianship or conservatorship,
- Patients unable to understand,
- Patients unable to read or write in French,
- Patients with communication difficulties or neuropsychiatric disorders,
- Patients with intolerance to nonsteroidal anti-inflammatory drugs,
- Patients with peripheral neuropathy,
- Patients with a history of allergy to local anesthetics,
- Patients with coagulation disorders,
- Patients with impaired renal function,
- Patients who chronically use opioids,
- Patients with chronic pain syndromes or fibromyalgia,
- Patients with an ASA score of 4.

6.3. Exclusion criteria

None

6.4. Recruitment procedures

All patients coming to the clinic for scheduled forefoot surgery who meet the eligibility criteria will be offered the opportunity to participate in the study. They will be informed during the anesthesia consultation. Informed consent will be obtained after taking the time to verify that the information provided has been properly understood. Patients unable to understand the content of the information provided will not be included in the study.

6.5. Simultaneous participation in another study, exclusion period

The patient may participate in another study simultaneously if the inclusion and exclusion criteria are met. There is no exclusion period for individuals participating in this study.

7. SAFETY ASSESSMENT

In the context of interventional research involving minimal risks and constraints, the medical procedures or strategies that are the subject of the research are part of standard practice and are used in accordance with their indications. Potential adverse events or incidents are therefore those related to the patient's routine care (care-related) and do not require specific reporting by the research coordinator.

These events must follow the standard reporting procedure established by current regulations and implemented within the institution:

- Adverse effects that may be related to a medication must be reported to the Regional Pharmacovigilance Center,
- Incidents or potential incidents resulting from the use of a medical device that must be reported to the local medical device vigilance coordinator,
- Other (reporting of nosocomial infections).

These reports are mandatory for all physicians (or other relevant healthcare professionals), both within the context of this study and outside of it.

As part of this study, the occurrence of adverse events will nevertheless be recorded and reported in the eCRF during a telephone call at Day 15±4 and during the follow-up visit with the surgeon at 1 month.

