5. RESEARCH METHODOLOGY

5.1. Study Type

Single-center, prospective, non-randomized, open-label study.

This is a pilot study seeking to demonstrate the feasibility of a specific block of the two distal branches of the tibial nerve for forefoot surgery, while preserving heel sensation.

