Based on the Practical Manual of Ultrasound-Guided Regional Anesthesia

Elsevier - Masson, Paris, 2014

Performing a superficial peroneal nerve block

E Albrecht, [name], H Cadas, V Moret.

adapted from Practical Manual of Ultrasound-Guided Regional Anesthesia
Published by Elsevier-Masson, Paris, 2014

- *Performing a saphenous nerve block*

An infiltration of the medial edge of the foot will be performed systematically.

- *Performing the specific lateral and medial plantar nerve block*

The line connecting the center of the medial malleolus and the medial calcaneal tuberosity (MC axis) will be marked prior to performing the block.

The ultrasound probe will be positioned at the medial edge of the foot below this line. The two plantar branches of the tibial nerve will be identified, as well as the tibial plantar arteries. The local anesthetic will be injected in contact with the neurovascular bundle.

The anesthesiologist will assess the identification of the plantar arteries and nerves below the MC axis using the ENR-Plantar Nerves protocol.

Position of the ultrasound probe for performing a block of the distal branches of the tibial nerve at the ankle

Sensory tests:

The cold test and touch test will be performed every 10 minutes for 40 minutes following the injection of local anesthetics into the specific territories of each nerve.

The anesthesiologist will record the sensory score for each branch of the tibial nerve.

At 40 minutes, a detailed sensory map of the sole of the foot will be created.

Recording of potential complications:

The occurrence of any paresthesia, indicative of nerve damage, will be noted. The anesthesiologist will ask the patient during the procedure about any sensations of discomfort: tingling, numbness, or other prickling sensations.

If regional anesthesia fails—defined as the inability to perform the surgery—the anesthesiologist will use the standard anesthesia technique: a tibial nerve block at the ankle above the mid-calf line.

b) Surgery

The surgical procedure will be performed according to standard practice.

Any intraoperative complications will also be noted.

The patient's satisfaction score will be assessed at the end of surgery.

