11.4. Legal obligations

11.4.1. Roles of the sponsor

The CMC Ambroise Paré is the sponsor of this study and is responsible for its conduct. The sponsor reserves the right to discontinue the study at any time for medical or administrative reasons; except in cases of force majeure, the investigator's opinion on this decision will be obtained and recorded in the trial documentation.

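### Section 7 waives specific adverse event reporting because the technique is standard practice, but the protocol tests a pilot block, names another as standard, and gives no route or timeline for notifying the sponsor of a procedure-related nerve injury.

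*Combined protocol and SAP*

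**What the plan says.** Section 7 of the protocol rests on one premise, that the procedures it studies "are part of standard practice and are used in accordance with their indications". From this it infers that adverse events belong to routine care and "do not require specific reporting by the research coordinator". It then lists the ordinary institutional channels. The first is "Adverse effects that may be related to a medication must be reported to the Regional Pharmacovigilance Center"; the others are device incidents, sent to the local device vigilance coordinator, and a residual line whose only example is nosocomial infection. The section closes by keeping a study record: "the occurrence of adverse events will nevertheless be recorded and reported in the eCRF", at the Day 15±4 call and the 1-month surgical visit. Sections 5.2.2, 5.3 and 12.5 add complications and paresthesia on the day of surgery.

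On the status of the block, section 5.1 states: "This is a pilot study seeking to demonstrate the feasibility of a specific block of the two distal branches of the tibial nerve". Section 5.2.2 says that if the study block fails, "the anesthesiologist will use the standard anesthesia technique: a tibial nerve block at the ankle".

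On authority, section 11.4.1 states: "The sponsor reserves the right to discontinue the study at any time for medical or administrative reasons".

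**The concern.** The reason given for the lighter reporting regime is that the technique is already standard. If the rest of the protocol treats it as unproven, the waiver has lost its stated basis, and the basis fails for the very block whose safety is under study.

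The practical stake is nerve injury. Section 5.2.2 treats paresthesia as a sign of nerve damage, and section 4.1 makes its absence part of the primary endpoint, so the authors see this as the relevant hazard. A persisting deficit after injection at a new site is the kind of event on which a sponsor might want to pause and look. The protocol gives the sponsor power to discontinue but does not say how it would learn of such an event, or how soon.

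**Working it through.** The plan gives no event rate and no figure on reporting, so the main check sets its sections side by side. A short calculation then shows what prompt notice could be worth.

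**1. Is the block under study standard practice?**

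- Section 7: yes, and this is why specific reporting is waived.
- Section 2.2: the approach below the line from malleolus to calcaneal tuberosity (the MC axis) is put forward as a hypothesis, something that might be considered.
- Section 3.1: its feasibility and safety are the primary objective.
- Section 5.1: the study is a pilot to demonstrate feasibility.
- Section 5.2.2: the fallback, a tibial block at the ankle, is what the protocol calls standard. The text places it above a mid-calf line, which may be a translation of the MC axis. On either reading it is not the study block.
- Section 2.3.2: the study is said to add no risks of its own, which is the same premise as section 7.

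Sections 2.3.2 and 7 therefore conflict with sections 2.2, 3.1, 5.1 and 5.2.2.

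**2. Where does a nerve deficit from the injection go?**

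- Vigilance channels (section 7): drug effects, device incidents, nosocomial infections. Injury from the injection procedure is not named.
- Study record: the eCRF, on Day 0, at Day 15±4 and at 1 month. No seriousness grading and no notification time is given.
- Sponsor: section 12.1 leaves the data under the trial staff's sole responsibility until they are transferred. The table in that section describes a form that tells the sponsor of each new inclusion. No counterpart is described for an adverse event.
- Monitoring (section 10.1): visits cover participant safety and data quality, but their frequency is not stated.
- Investigator (section 5.7): may suspend an individual's participation. The block is given once, on Day 0, so doing this after a deficit is found does not affect later patients.
- Section 8.4: no interim analysis that could stop the study.

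**3. How much could prompt notice change?**

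Inputs: 50 patients (section 8.2), 23 months of enrollment (section 5.4), first postoperative contact at 11 to 19 days (15±4). Even enrollment is assumed.

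- Rate: 50/23 = 2.17 patients per month. With 365/12 = 30.4 days per month, this is 2.17/30.4 = 0.0715 per day.
- Treated before the Day 15±4 contact: 0.0715 × 11 = 0.8 to 0.0715 × 19 = 1.4 patients.
- Treated before the 1-month visit: about 2.2 patients.
- Illustration: a deficit in the fifth patient, found at the call, leaves 50 − 5 − 1.4 = 43.6 to 50 − 5 − 0.8 = 44.2, so about 44 patients still to be treated.

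**4. How many events might there be?**

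The true rate p is assumed. The chance of at least one event in 50 is 1 − (1 − p)^50:

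- p = 1%: 39%
- p = 2%: 64%
- p = 5%: 92%

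If none is seen, the exact two-sided 95% upper limit is 1 − 0.025^(1/50) = 7.1%. At low rates events would be few, and a series of 50 cannot exclude a rate of several percent. How each single event is handled therefore matters more than any tally at the end.

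**The case against.** The strongest reply is that events are neither hidden nor lost. A reader might infer from section 7 that adverse events are exempt from reporting to the study. They are not: what is waived is specific reporting by the research coordinator, and the same section keeps eCRF recording. A reader might also infer that nobody able to act is told. That too goes beyond the text. The anesthesiologist asks about paresthesia during the block, the surgeon sees the patient at 1 month, data are entered as they are obtained (section 10.2), and a sponsor-appointed monitor checks participant safety. The study is single-center, and the sponsor's own IT department secures data transmission, so sponsor and site appear to be the same institution.

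Nor do the documents show that a nerve deficit falls outside every vigilance route. Ropivacaine is injected beside each nerve through a regional-anesthesia needle, so a deficit could be reported as possibly related to the drug or the device. All that can be said is that procedural nerve injury is not named. The idea that a run of deficits would surface only at analysis is a worst case: section 8.4 rules out an interim statistical analysis, not a review of safety.

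An alert on every positive questionnaire answer would also serve poorly. Question 1 of Appendix 1 asks about any reduced sensitivity since surgery, with no duration, and the intended block itself causes that.

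All of this stands, and it limits the point. It does not supply a route or timeline to the sponsor, and it does not repair the premise.

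**Conclusion.** The point holds in two parts. First, section 7 bases its waiver on a premise that sections 2.2, 3.1, 5.1 and 5.2.2 contradict. This is a conflict in the text, not merely a missing detail. Second, events are recorded and visible to investigators, but no stated route or timeline brings a procedure-related nerve injury to the sponsor, which holds the authority to discontinue.

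The size is best expressed as opportunity. Under even enrollment only one or two further patients would be treated before a deficit is first asked about by telephone, so notice at that time could inform nearly all remaining inclusions. This measures neither harm nor its likelihood, because the documents give no event rate.

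The documents do not support the further inference that the minimal-risk category is legally wrong. That depends on rules outside them and is a matter for the ethics committee. The correction should be made, but nothing here shows that participants would go unobserved.

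**What to change.** Reconcile section 7, and the statement in section 2.3.2 that the study adds no risks, with sections 2.2, 3.1, 5.1 and 5.2.2, so that the reporting waiver no longer depends on the study block being standard practice. If this affects the stated basis for the minimal-risk category, put the question to the ethics committee with the amendment.

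Then state in section 7 that three kinds of event are notified to the coordinating investigator and the sponsor when entered in the eCRF:

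- intraoperative nerve-related complications;
- sensory-motor deficits still present at the Day 15±4 or 1-month contact, as distinct from the expected transient block;
- serious events.

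Have the sponsor's review of each documented under section 11.4.1. Because question 1 of Appendix 1 does not separate past from persisting loss, add a follow-up item asking whether it is still present. Keep the existing vigilance channels. No stopping threshold is proposed.

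The cost is revised wording, one questionnaire item, an eCRF alert and a small amount of documentation. No extra patients or visits are needed.
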